9.3 Variables

Demographics

Basic demographics including patient initials, age (year and month of birth), sex, weight, height, name of institution, department and physician will be taken and recorded.

Diagnosis and Medical History

Diagnosis and medical history including previous TB history or vaccination, will be taken and recorded and will include the following items to get patient's medical status:

- CD related history ; date of pediatric CD diagnosis, involved intestinal area, presence of draining fistula, previous CD related therapy including antibiotics, steroids, 5-ASA, Immunosuppressants, biologics and nutritional therapy
- Previous TB history ; presence of TB, TB treatment regimen received, completeness and appropriateness of the therapy regimen, vaccination
- Other medical history ; history of previous disease(s), concurrent disease(s), history of allergy, pregnancy etc.

PPD Skin Test

PPD skin test will be performed and recorded. It will include: Date of PPD test, induration at PPD test site (in mm). (Refer to MFDS Guideline for Latent TB Management in TNF-Antagonist Use and TB screening Aide provided by AbbVie.)

Chest X-ray

Chest X-ray interpretation result will be taken and recorded and will include: Date of Chest-X-Ray, presence of latent or active TB lesion. (Refer to MFDS Guideline for Latent TB Management in TNF-Antagonist Use and TB screening Aide provided by AbbVie.)

Interferon gamma release assay

Interferon gamma release assay will be performed, recorded and will include: date of interferon gamma release assay and result. (Refer to MFDS Guideline for Latent TB Management in TNF-Antagonist Use and TB screening Aide provided by AbbVie.)

Treatment with Humira®

Patients will be administered Humira® as per the package label. Unit dose, frequency, length of treatment (start date, end date) will be recorded on the appropriate case report form.

Concomitant Medication

Concomitant medications, including TB prophylaxis regimen, corticosteroids, immunosuppressants, will be recorded and will include: generic name (brand name in case of combination drug), total daily dose, length of administration (start date and end date), indication(s).

Safety (Adverse Event)

Regardless of results of causality assessment, presence of adverse event(s), type of adverse event(s), onset, end date, severity, causality assessment by physician on the adverse event(s), action taken, outcome will be captured, during the study, from the first administration to the surveillance period (from informed consent to up to 70 days following the last administration of Humira®) (Section 11.0 Management and Reporting of Complaints).

Effectiveness

From the patients treated with Humira®, the effectiveness data (i.e. PCDAI score) at previous times before Humira® treatment, at 4 weeks (visit window: ± 1 week) and at 6 months (visit window: ± 4 weeks) post-treatment will be collected. (CDAI score will be collected as well, if possible.)

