9.2 Setting

Selection of Study Population

Pediatric CD patients who has been prescribed Humira® by the treating physician as per Korean label will be enrolled.

The patients who are receiving Humira® for pediatric CD during study period and meet the inclusion /exclusion criteria will be enrolled in the sites which signed a contract with AbbVie.

Once the study agreement is in place, the surveillance will be initiated at the site, and all patients who are prescribed Humira® for pediatric CD treatment during the surveillance period and who meet the inclusion /exclusion criteria will be enrolled in the study until the assigned number of subjects are registered at the site.

Inclusion Criteria

1. Pediatric patients with Crohn's Disease who are prescribed Humira in accordance with the Korean label for Humira authorization (labeling)
2. Patients who have given written authorization or patients whose legal representatives have given it to use their personal health data for the purposes of this study.

Physician will refer to the product market authorization (label) for inclusion criteria.

Exclusion Criteria

Patient with any of the following should not be registered in this surveillance:

1. Any contraindications to Humira as listed on the approved product market authorization (labeling)
2. Patients who is participating on other clinical trials.

Patients will be observed for 6 months following first dose of Humira®.

It is planned to include all patients who are treated with Humira® until the planned number of cases are collected to obtain meaningful safety data including TB incidence in the early stage of the study conduct. Once this study has been initiated in an institution, physicians are recommended to include/recruit all eligible patients who are prescribed Humira®.

An evaluable patient is a patient who has been administered Humira® at least once and has safety information at subsequent visits. (or telephone contact, correspondence)

Drop-out patients also will be considered for safety evaluation, if the safety information is obtained by follow-up contact. If there is loss of follow-up, the reason will be recorded.

Investigator Selection Criteria

The surveillance will be conducted in medical institutions in Korea. The institutions include clinics and hospitals. The physician must meet the following criteria:

1. A physician who is working in a hospital or clinic and has a patient pool eligible for this surveillance.

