9.7 Data Analysis

Justification for the planned sample size

Information on at least 600 subjects will be collected in this surveillance study in accordance with the Korean regulations on New Drug Re-examination (i.e. New Drug Re-examination Standards: Ministry of Food and Safety (MFDS)).

The sample size of 600 has been selected in order to give at least 95% probability of detecting at least one uncommon SAE that occurs in the Korean patient population at a rate of at least 0.5%. This estimate is based on the assumption that the occurrence of AEs has a Poisson distribution and that if the population rate of occurrence of an AE is 0.5% then the expected number of AEs in the proposed sample size of 600 would be 3. The probability of observing 1 or more events with a Poisson parameter of 3 is 0.95 or 95%.

If we have an AE with a population probability of 0.5% then the expected number of events in a sample size of 600 will be 3. Using the Poisson Distribution with a parameter of 3 the probability of getting zero AEs in our sample size of 600 is given by the formula:

$$\Pr\{X = 0\} = \frac{3^0 \times e^{-3}}{0!} = 1 \times 0.0498 = 0.0498$$

The probability, therefore, of having 1 or more AEs in that sample size is $1 - 0.0498 = 0.9502$.

At least 600 subjects were to be collected for surveillance to meet the local regulatory requirements, but number of subjects to be enrolled was adjusted to 141 subjects. (Refer to section 9.5)

Analysis Population

Number of collected and analyzed patient will be presented as following items: Contracted cases, collected number of CRFs, safety-evaluable cases, effectiveness-evaluable cases, number of drop-out cases, Reasons for drop-out

The safety analysis data set will include all subjects who have received at least one administration of Humira® following the initiation of surveillance and have completed follow up for the safety information.

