For induction effectiveness of Humira®, the effectiveness analysis data set will include all subjects who have been administered Humira® and prescribed Humira® for 4 weeks including induction period (± 1 week) and for whom effectiveness evaluation parameters have been recorded. And for maintenance effectiveness of Humira®, effectiveness analysis data set will include all subjects who have been administered Humira® and prescribed Humira® for 6 months (± 4 weeks) and for whom effectiveness evaluation parameters have been recorded. The subjects whose effectiveness evaluation was not properly conducted because their data from evaluation parameters were missing or they discontinued administration prior to the effectiveness evaluation will be excluded from the evaluation.

Safety Analysis

The adverse events will be coded by MedDRA dictionary. The number and percentage of subjects reporting any serious adverse events/adverse drug reactions will be tabulated overall and by MedDRA 17.0 or more recent version, in preferred term. The number and percentage of subjects reporting unexpected (unlabeled) adverse drug reactions will be tabulated in a similar fashion.

To investigate the factors affecting the safety, the number and percentage of subjects reporting adverse events will also be classified by various background factors (e.g., demographic factors, treatment factors such as medical history, dosing and administration, concomitant medications, beginning of administration before/after the registration date, etc.) and tabulated. If the incidence of adverse events in the subjects who began the administration before/after the registration date has statistical significance, it will be presented as a separate item. In addition, if there are patients who have already been

administered Humira® when participating in the surveillance, their adverse events from the first administration of Humira® to the inclusion will be presented in a separate table. If data from special patient groups are collected, they will be extracted and tabulated separately for adverse events/adverse drug reactions.

Effectiveness Analysis

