10.0 Protection of Human Subjects

Patient written authorization form to use and/or disclose personal and/or health data from legal patient or representative must be obtained prior to enrolling the patient and the physician is required to document this authorization.

However, informed consent will not be required because as local pharmaceutical law does not require informed consent for regulatory-required post-marketing surveillance.

Patient confidentiality must be maintained at all times; therefore demographics that could identify the patients will not be collected.

Monitoring for any sites is not required. However internal consistency check for completeness and consistency of data will be done to ensure integrity of the information reported.

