11.1.4 Serious Adverse Event Collection Period

Serious adverse events will be reported to AbbVie from the time the physician obtains the patient's authorization to use and disclose information (or the patient's informed consent) until 70 days or 5 half-lives following the intake of the last dose of physician-prescribed treatment.

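### Sections 9.2 and 9.3 end adverse event follow-up at different times, 9.7 names no analysis window, and the planned before/after-registration test takes no account of time at risk.

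*Combined protocol and SAP*

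**What the plan says.** - **Observation period.** Section 9.2: "Patients will be observed for 6 months following first dose of Humira".
- **Adverse event capture.** Section 9.3 ties capture to the duration of the study and gives the period as "from the first administration to the surveillance period (from informed consent to up to 70 days following the last administration of Humira". No limit at month 6 is stated there. The same section collects effectiveness data "at 6 months (visit window: ± 4 weeks) post-treatment will be collected".
- **Drop-outs.** Section 9.2: "Drop-out patients also will be considered for safety evaluation, if the safety information is obtained by follow-up contact". The safety set in 9.7 asks for completed safety follow-up without saying when follow-up is complete.
- **Summaries.** Section 9.7 plans numbers and percentages of subjects, with chi-square or Fisher tests by background factor. It also plans an incidence rate with a 95% CI over the whole surveillance, without a stated denominator.
- **Start before or after registration.** This is one of the named background factors. "If the incidence of adverse events in the subjects who began the administration before/after the registration date has statistical significance", the result is reported as a separate item. Events that earlier starters had between first dose and inclusion go into a table of their own.
- **Numbers.** Section 9.5, Table 2, expects 141 subjects: 71 + 31 = 102 who start Humira after enrolment and 29 + 10 = 39 who start before it.

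**The concern.** A percentage of subjects with an event has meaning only with a period attached. Section 7.0 compares the safety data with the label, and section 8.0 hypothesises consistency with phase 3. Both comparisons need that period.

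The before/after comparison is the most exposed. The two groups differ by definition in when first dose falls relative to inclusion. If pre-inclusion events are left out and follow-up stops 6 months after first dose, earlier starters have less time at risk. If events count from first dose with no cap, they may have more. A test on percentages can then be significant when the hazards are equal, and 9.7 attaches a reporting consequence to significance.

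**Working it through.** **The plan's own figure.** The sample size justification in 9.7 uses a 0.5% event rate in 600 subjects: 600 × 0.005 = 3, and 1 − exp(−3) = 0.9502, as stated. This calculation ("if the population rate of occurrence of an AE is 0.5"%) has no time unit, so the plan already uses the word rate for a plain proportion. The later incidence rate could be either a proportion or a person-time rate.

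**Assumptions, none given in the documents.** Constant hazard r of a first event, equal in both groups, at 0.2, 0.5 or 1.0 per patient-year; last dose at month 6 for the window comparison; a two-sided 5% level; the times at risk shown.

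**1. Effect of the window.** P(at least one event) = 1 − exp(−r·t), with t = 0.5 years, or t = 0.5 + 70/365.25 = 0.692 years. At r = 0.5: 1 − exp(−0.25) = 22.1% and 1 − exp(−0.346) = 29.2%.

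| r per year | 6 months | 6 months + 70 days | subjects of 141 |
|---|---|---|---|
| 0.2 | 9.5% | 12.9% | 13 vs 18 |
| 0.5 | 22.1% | 29.2% | 31 vs 41 |
| 1.0 | 39.3% | 49.9% | 55 vs 70 |

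The longer window is 0.692/0.5 = 1.38 times the shorter. If treatment continues past month 6, the 9.3 window is longer still and varies by subject.

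**2. Before/after test, 102 vs 39.** For x events among 102 and y among 39, with P = (x + y)/141, uncorrected chi-square rejects when |x/102 − y/39| / √[P(1 − P)(1/102 + 1/39)] > 1.96. Each group's count is binomial with probability 1 − exp(−r·t). Summing the probabilities of all (x, y) that reject gives:

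| Time at risk, earlier vs new starters | r = 0.2 | r = 0.5 | r = 1.0 |
|---|---|---|---|
| 6 vs 6 months | 4.8% | 5.1% | 5.1% |
| 5 vs 6 (pre-inclusion events out, 1-month lag to enrolment) | 4.4% | 6.4% | 8.6% |
| 3 vs 6 (pre-inclusion events out, 3-month lag) | 9.2% | 27.0% | 49.8% |
| As the row above, both groups followed 70 days longer | 8.4% | 19.2% | 32.6% |
| 12 vs 6 (events counted from first dose, no cap) | 31.2% | 54.2% | 72.5% |

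Fisher's test is a little lower: 3.3%, 3.5% and 3.6% with equal follow-up, and 6.4%, 23.0% and 45.6% in the third row.

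**3. Whether a rate alone is enough.** Simulated, with new starters followed in months 0–6 and earlier starters in months 3–9, an exact rate test rejects in 4.2% of studies at a constant 0.5 per year. It rejects in 24.9% if the hazard is 0.75 per year in the first 3 months and 0.25 after. Comparing the groups within the same interval since first dose rejected in about 2–5% over the hazard patterns tried. A rate therefore removes unequal follow-up but not a hazard that changes over treatment.

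**The case against.** The best defence is that the sections can be read together: events are captured during the study, a subject is observed for 6 months, and the 70 days are only an outer limit after the last dose. That reading is possible, but 9.7 does not adopt it, and a subject still treated at month 6 has two candidate end dates.

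It can also be said that 9.7 already handles earlier starters, by naming the factor and giving pre-inclusion events their own table. This is partly right. The table is described as an addition, which does not settle whether the same events enter the main percentages. Showing the groups apart does not equalise their time at risk.

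The requirement for completed safety follow-up may limit unequal follow-up, but cannot be applied consistently until the end of follow-up is fixed.

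Three stronger readings are tempting and not supported:

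- A reader might infer that 9.3 gives two contradictory start points. The bracket there defines the surveillance period. Capture from first dose fits the separate pre-inclusion table in 9.7. The wording is clumsy rather than contradictory.
- Section 10.0 says "informed consent will not be required", so a window that starts at consent may look void. But written authorization is obtained, and 11.1.4 treats authorization and consent as alternatives.
- Section 11.1.4 collects serious events "until 70 days or 5 half-lives following the intake of the last dose of physician-prescribed treatment". That is a reporting period and may legitimately differ from an analysis window.

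**Conclusion.** The point holds as a gap in the analysis plan that should be closed before the final analysis. The ends of follow-up in 9.2 and 9.3 differ for subjects still treated at month 6, and 9.7 fixes neither the window nor the place of pre-inclusion events.

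If the last dose is at month 6, the choice of window adds 3 to 11 percentage points to the proportion with an event over the hazards tried. The before/after test can be significant from follow-up alone, in either direction.

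A reader might infer that this test will be biased. The documents do not show that. The 9–50% figures need pre-inclusion events excluded, a 6-month cap from first dose and a 3-month lag together. The 31–73% figures need earlier starters to have twice the time at risk. With equal follow-up the test behaves properly, and with a 1-month lag the inflation is small (4–9%). Which case applies depends on wording the plan has not settled. All sizes rest on assumed constant hazards and assumed times at risk.

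**What to change.** 1. Reconcile the ends of follow-up in 9.2 and 9.3.
2. In 9.7, name one per-patient window for adverse event analysis, with its start and end. State whether pre-inclusion events are in or out of the main tables, and whether the incidence rate is a proportion or a person-time rate.
3. Keep the percentages. Add subjects with a first event in the window per 100 patient-years, with exact Poisson 95% CIs, overall and by start before or after registration. End time at risk at the earliest of first event, end of window, 70 days after last dose, or last safety contact. If pre-inclusion events are out, earlier starters enter at their enrolment date.
4. Base the before/after comparison on the same interval since first dose, or stratify by that interval. For this factor, let it replace the unadjusted significance trigger in 9.7. Label it descriptive, because earlier starters are selected for still being on Humira at enrolment.

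The cost is wording in 9.2, 9.3 and 9.7, one extra set of tables, and a check that the CRF gives a last-safety-contact date. Treatment start and end dates and event onset are already recorded under 9.3. Rates for the other background factors are optional. The consent wording in 10.0 and the reporting period in 11.1.4 need no change.

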9.4 Data Sources

Case Report Forms will be supplied by AbbVie Korea. These forms will be used to transmit information collected during this study to AbbVie Korea. Case report form must maintain pertinent patient background information, e.g., gender, age, medical history, and the information to be evaluated. The case report form must maintain patient confidentiality, e.g. patient names must not be collected (patient initials are acceptable) and date of birth must not be collected (age or month and year of birth are acceptable). The physician or staff under his/her supervision must complete the case report forms and neither AbbVie nor any agents acting on behalf of AbbVie may complete the case report forms.

9.5 Study Size**Number of Patients to be enrolled**

At least 600 subjects were to be collected for surveillance to meet the local regulatory requirements, but the number of subjects was adjusted to 141 subjects based on the followings:

1) Significantly low incidence and prevalence of Pediatric CD

Based on the data obtained from 1996 to 2002 in North America, 93.6 per 100,000 people suffered from Crohn's disease and the incidence rate of Crohn's disease in children aged less than 18 years was 3.0 per 100,000 people.¹⁸ Additionally, it is reported that when considering the ethnic differences, Crohn's disease is more prevalent in developed countries and relatively less common in Asia;¹⁹ for example, a retrospective study conducted in China revealed that the prevalence of Crohn's disease was estimated to be 1.4 per 100,000 people,²⁰ which was much less than that reported in North America.

According to the data reported to Korea Health Insurance Review & Assessment Service in 2015, the number of patients aged 19 years or younger who are with 'K50: Crohn's disease [regional enteritis]' was only 3,051. Considering that ages eligible for enrollment in this Post-Marketing Surveillance are between 6 years and 17 years according to its approved label in Korea, it is expected that the number of patients eligible for this Post-Marketing Surveillance would be much less than the number aforementioned, but there is no specific domestic data to prove it in Korea.

2) Humira is not a primary therapeutic agent for Pediatric CD

Humira® is indicated only to patients with severely active Crohn's disease with inadequate response, intolerance, or contraindication to primary trophotherapy, corticosteroids and/or immunomodulators according to the approved label, which is reflected in the very limited number of patients with Crohn's disease of all ages who received treatment with biologics, based on the data reported to Korea Health Insurance Review & Assessment Service [Table 1].

[Table 1] The estimated number of patients diagnosed with Crohn's disease and proportion of those patients with anti-TNF agents prescription

	The number of patients diagnosed*	Patients prescribed with anti-TNF agents	
		The mean number of patients†	% ‡
All ages	17,651	1,684	9.5%

* The number of patients diagnosed: The number of patients diagnosed in 2015 according to the disease code (K50: Crohn's disease [regional enteritis]); source: Health Insurance Review & Assessment Service; unit: people

† The mean number of patients: The number of patients prescribed with anti-TNF agents for relevant disease codes (K500, K501, K508 or K509); source: Health Insurance Review & Assessment Service; unit: people

‡ Percent: calculated by dividing the mean number of patients by the number of patients diagnosed

3) Difficulties in getting patients' consents

Pediatric CD is indicated for pediatric patients, it is difficult to get pediatric patients' consents from their parents.

However, we will make every effort to enroll maximum number of subjects. We expect maximum 141 patients will be recruited [Table 2].

[Table 2] The number of subjects expected to be enrolled in this study

Classification	No. of subjects
Enrolled subjects as of October, 2016	100
- subject who start Humira treatment after enroll in the study	71
- subject who starts Humira treatment before enroll in the study	29
Estimated No. of subjects to be enrolled	Approx. 41
- subject who will start Humira treatment after enroll in the study	31*
- subject who starts Humira treatment before enroll in the study	10
Total	Approx. 141

* Calculated as follows: 5.07 (mean number of newly diagnosed patients per month) x 6 months (remaining enrollment period) = 30.42

About 15 investigators across the country will be participating in this surveillance and the number of subjects to be collected by each investigator will vary.

Study Duration

The study duration designated by MFDS is from 12 September 2013 to 11 September 2017. The study will start after the launch of the product as a new drug for pediatric CD and the final report will be submitted to MFDS by 11 Dec 2017. Interim study reports will be submitted to MFDS every 6 months for the first 2 years, then annually thereafter during PMS period.

